7.4. The randomisation scheme

Participants will be allocated to receive either Brensocatib (25mg once daily for 28 days) or placebo in addition to standard of care. Randomisation will be 1:1 intervention:placebo. Randomisation will be stratified by site and age: <65 years/≥65 years.

7.4.1. Method of implementing the randomisation/allocation sequence

After successful completion of screening the participant will be assessed for eligibility for randomization. This will be documented in the electronic Case Report Form (eCRF).

Participants will be randomised by the PI or delegate to one of the two treatment regimens as noted in Section 8.1.

The PI or delegate will use a centrally controlled web-based GCP compliant randomisation system, TRuST, run by the UKCRC registered Tayside Clinical Trials Unit (TCTU). TRuST is provided by the Health Informatics Centre, University of Dundee. TCTU use a validated randomisation program and will securely backup both the randomisation seed and the randomisation allocation. TRuST will provide an immediate allocation on screen and confirmation of allocation will be emailed to the site PI, person completing randomisation and clinical trials pharmacy. The trial manager, data manager and CI will receive treatment allocation emails for all participants at all sites.

Access to be able to randomise a participant will only be given after completion of appropriate training.

7.5. Blinding

Double-blind, placebo-controlled Participants will be allocated via the randomisation system to receive either active treatment or matching placebo, see section 8.1 The active treatment/placebo will be packaged and labelled so as to not identify the contents. Trial staff and participants will be blind to the allocation received. The final unblinding of the treatment allocation will occur after the creation of a final locked database.

7.6. Emergency Unblinding

TCTU will provide each PI with a login to the interactive web-based randomisation system, Tayside Randomisation System (TRuST), for 24-hour emergency unblinding at their site only. The CI will also have access to unblind participants at all sites. The date, reason and result will be documented and signed by the person carrying out the unblinding. This will be stored in a sealed envelope in the ISF. Disclosure of the unblinding result will be to individuals involved in the participant's care only. Where possible, the participant will remain in the trial and continue with the trial procedures.

In addition, a paper copy of the allocation will be stored securely in NHS Tayside Clinical Trials Pharmacy. Unblinding will only be carried out where a physician considers that it is necessary for clinical safety.

7.7. Baseline data

Baseline data will be collected as per Schedule of Procedures, Appendix 4, and as described below, section 7.8. Only information directly related to the objectives and outcome measures detailed in the protocol shall be collected.

7.8. Trial assessments

Trial assessments will be performed according to the Schedule of Procedures, Appendix 4.

After informed consent, the following assessments will be reviewed to determine eligibility requirements as specified in the inclusion and exclusion criteria:

- Focused medical history, taken from medical records, including the following information:
 - Approximate day of onset of COVID-19 symptoms
 - History of chronic medical conditions related to inclusion and exclusion criteria
 - o Medication allergies
 - Review medications and therapies for this current illness
- Review recent radiographic imaging (x-ray or CT scan)
- Physical examination findings
- SpO₂ on air
- Obtain blood for screening laboratory evaluations if not done in the preceding 72 hours:
 - ALT
 - AST
 - o Creatinine
 - o eGFR
 - Lymphocyte count

Clinical screening laboratory evaluations will be performed locally by the site laboratory. The overall eligibility of the participant to participate in the trial will be assessed once all screening values are available. The screening process can be suspended prior to complete assessment at any time if exclusions are identified by the trial staff. Equally, if a patient qualifies for participation based on one inclusion criteria of severe, e.g requirement for supplemental oxygen, it is not necessary to perform a physical examination to confirm the presence of rales or crackles as the patient is already eligible. Trial participants who qualify will be immediately randomized.

It is likely that the above assessments to confirm eligibility will be carried out by the clinical team during routine care of patients being assess for COVID-19. Where these assessments have been carried out by the clinical team in the preceding 72 hours, the most recent of these results will be used to prevent duplication and further exposure of the trial staff to patients with COVID-19. If any screening procedures have not been carried out in the previous 72 hours (96 hour for positive SARS-CoV-2 test) hours for these will be completed by the trial staff. Screening procedures will only be recorded/carried out after consent.

For all baseline assessments and follow-up assessments, refer to Schedule of Procedures for procedures to be done, and details below for each assessment.

Clinical Assessments

It is expected that these clinical assessments will be carried out by the clinical team during routine clinical care and documented on a NEWS chart. Where the assessments have been carried out, the results of the assessment closest to 8am on the day will be used to prevent duplication and further exposure of the trial staff to patients with COVID-19.

- Blood pressure and pulse, lying or seated
- Tympanic temperature
- SpO2
- Record if SpO2 has been measured on air or oxygen concentration the participant was receiving.

Ordinal Scale

The ordinal scale is an assessment of the clinical status on a given trial day. Each day, the worst score for that day will be recorded. The scale is as follows:

- 1. Not hospitalised, no limitations on activities
- 2. Not hospitalised, limitation on activities;
- 3. Hospitalised, not requiring supplemental oxygen;
- 4. Hospitalised, requiring supplemental oxygen;
- 5. Hospitalised, on non-invasive ventilation or high flow oxygen devices;
- 6. Hospitalised, on invasive mechanical ventilation or ECMO;
- 7. Death.

NEWS Score

The NEWS score has demonstrated an ability to discriminate patients at risk of poor outcomes. (Smith, 2016). This score is based on 7 clinical parameters. The NEWS2 Score is being used as an efficacy measure.

This should be evaluated at the assessment recorded closest to 8am on a given trial day. These parameters can be obtained from the hospital chart.

Exploratory assessment- viral shedding

Where practical at the Tayside site only, nasal swabs will be obtained on day 15 and day 29 to evaluate viral clearance by PCR.

Exploratory assessment- neutrophil studies

At the Tayside and Sheffield sites only, additional blood will be taken for isolation of peripheral blood neutrophils, as per outcome measures section 3.7.

Exploratory assessment- quality of life

The validated EQ-5D-5L quality of life tool will be administered to patients who are able to complete the questionnaire either in person (those still in hospital) or over the telephone (those at home) to determine the impact of treatment on quality of life.

Clinical Evaluation

As these participants are in-patients receiving care for COVID-19, they will be monitored as per clinical need. Where already obtained for clinical need the following blood results will be recorded at days 1, 3, 5, 8, 11, 15, 29:

- White cell count, haemoglobin, platelets, neutrophils, eosinophils, lymphocytes
- creatinine, eGFR
- AST and ALT

Participants discharged home will not receive further safety assessments. It is not necessary to perform further blood tests on inpatients for the purposes of safety. Routine blood tests taken as part of routine clinical care will be used. If tests are not performed for clinical reasons they will be treated as missing data for analysis.

7.9. Long term follow-up assessments

Participants will receive long term clinical follow-up as deemed appropriate by local clinical teams.

7.10. Qualitative assessments

N/A

7.11. Withdrawal criteria

Participants are free to withdraw at any time and are not obliged to give a reason(s). The CI, PI or delegate will make a reasonable effort to ascertain the reason(s), both for those who express their right to withdraw and for those lost to follow-up, while fully respecting the individual's rights.

The PI may withdraw a participant at any time if it felt to be in the best interest of the participant and treatment continuation would be detrimental to the participant's wellbeing. In addition, the trial drug will be discontinued in the following circumstances:

- Persistent adverse effects which are determined to be severe, persistent, treatment-related and not responsive to treatment
- If an allergic reaction to trial drug occurs, the trial drug will be stopped and treatment will be initiated as appropriate
- Absolute neutrophil count less than 1.0 x 10⁹ cells per L at any time.

A full explanation for discontinuation of trial drug will be provided to the participant. As the trial is being conducted on an intention to treat basis, if the participant has been randomised and given one or more dose of IMP, s/he will be asked to complete trial assessments as per the protocol, if the CI/PI considers it appropriate, to allow for an intention to treat analysis, but will be censored in the per-protocol analysis. Participants are free to refuse to do so. Withdrawn participants will not be prescribed trial drug.

Those withdrawn, including those lost to follow-up, will be identified and a descriptive analysis of them provided, including the reasons for their loss, if known, and its relationship to treatment and outcome.

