True odds ratio	Total sample size
1.5	774
1.75	412
2.0	272
2.25	201
2.5	159

Table 6. Treatment ordinal outcome proportions under odds ratio of 2 for scenario in Table 4 at day 15.

Anticipated						
Severity Outcome	Control %	Treatment %				
Death	2	1				
Hospitalised, on mechanical						
ventilation or ECMO	1	0.5				
Hospitalised, on non- invasive						
ventilation or high	2	1				
flow oxygen devices						
Hospitalised, requiring	7	3.8				
supplemental oxygen						
Hospitalised, not requiring	8	4.7				
supplemental oxygen						
Not hospitalised, limitation on	38	29.7				
activities						
Not hospitalised, no	42	59.2				
limitations on activities						

Note that columns may not sum to exactly 100 due to rounding errors.

Prior to the commencement of the trial, we took the anticipated WHO scenario and the odds ratio of 2 which required enrolment of 272 participants. Allowing for a potential loss to follow-up of 9% (27 participants) this meant we will required 300 participants (150 per arm) to achieve 85% power at 5% significance. This was subsequently reviewed as part of a pre-specified blinded sample size re-evaluation by an independent statistician. The results of this re-evaluation, using data for the primary endpoint available in December 2020 found that 300 patients enrolled would provide approximately 88% power to detect an odds ratio of 2.0. This, along with the results of other COVID-19 trials were reviewed by the Trial Steering Committee (TSC) and DMC who noted that other COVID-19 therapeutics had achieved odds ratios lower than 2.0 in the majority of cases. Based on this, the TSC and DMC recommended targeting an odds ratio of 1.75. At least 80% power for an odds ratio of 1.75 requires enrolment of a minimum of 360 patients with 400 patients provided approximately 85% power. A final sample size of 400 subjects was therefore recommended by the TSC and subsequently approved by the DMC in December 2020. Planned recruitment rate

Recruitment is expected to be completed by the end of January 2021.

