10.2. Statistical analysis plan

The primary analysis will be based on an intention-to-treat population, including participants randomized. Similarly, safety analyses will be based a modified intent-to-treat population consisting of all participants who were randomized.

This is a controlled randomized trial testing a superiority hypothesis with a two-sided type I error rate of 0.05. Secondary hypotheses have been ordered according to relative importance. These will be described according to the appropriate summary statistics (e.g., proportions for categorical data, means with 95% confidence intervals for continuous data, median for time-to-event data).

A statistical analysis plan (SAP) will be prepared for analysis of primary and secondary outcomes and will include a plan for handling missing data.

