## 7.4 Missing Data

(ICH E3; 9.7.1, 11.4.2.2. ICH E9;5.3. EMA Guideline on Missing Data in Confirmatory Clinical Trials)

All reasonable efforts will be taken to minimise loss to follow-up, which is expected to be minimal as data collection for primary and secondary outcomes using trial-specific eCRFs is combined with linkage to routine clinical data on study outcomes. The number and percentage of participants with follow-up information at day 29 after the randomisation will be reported. For all participants who were discharged and alive but have missing clinical status, a clinical status scale of 2 (Not hospitalised, limitation on activities) will be applied.

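### Outcome collection after stopping trial drug is left to investigator judgement, which can create informative missing day-29 data that the SAP handles only in part, with an untested single-value fill

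*Protocol*

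**What the plan says.** Protocol 7.11 (Withdrawal criteria) sets two conditions for outcome collection after trial drug is stopped. The participant must have been randomised and had at least one dose, and will then be asked to complete assessments "if the CI/PI considers it appropriate, to allow for an intention to treat analysis". The participant's own right to refuse is stated separately, so the investigator's judgement is an additional condition. The same section requires a descriptive analysis of withdrawals, including how loss relates to treatment and outcome.

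Protocol 10.2 states: "The primary analysis will be based on an intention-to-treat population, including participants randomized". Protocol 10.5 and SAP 7.2.1 instead limit the analysis to participants who had at least one dose.

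On missing outcomes, SAP 7.4 says that for participants discharged and alive without a recorded status, "a clinical status scale of 2 (Not hospitalised, limitation on activities) will be applied". It expects little loss because eCRF data are combined with linkage to routine records. Protocol 10.5 allows multiple imputation where missing at random is plausible, and commits to a complete-case analysis as a secondary analysis. The SAP mentions neither.

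**The concern.** Intention to treat needs the outcome of every participant in the analysis set, whether or not drug is continued. Under Protocol 7.11 drug is stopped for persistent severe treatment-related effects, allergic reaction, low neutrophils, or the investigator's view of the participant's interest. These reasons can differ between arms and can be related to prognosis. A discretionary decision not to seek assessments from such participants can therefore produce missing data that are neither random nor balanced.

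Records can repair part of this. Deaths and in-hospital status are documented without the participant's help. The difference between categories 1 and 2 is whether activities are limited. For a discharged participant that comes from the day-29 contact, which is a telephone call at most sites and a visit at Tayside and Sheffield. If that contact is not made, linkage is unlikely to supply the answer. The planned placebo distribution puts 42% in category 1 and 38% in category 2, so the loss falls where most of the outcomes lie. A single filled value then feeds into the primary odds ratio, and no planned analysis tests it.

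**Working it through.** **Inputs from the documents.** Allocation is 1:1, with a "two-sided type I error rate of 0.05". The planned placebo distribution for categories 1 to 7 is 42, 38, 8, 7, 2, 1, 2% (Protocol 10.1, Table 4). On the design target, "the TSC and DMC recommended targeting an odds ratio of 1.75", and "400 patients provided approximately 85% power".

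**Inputs assumed.** The documents give no rate of stopping drug, of investigator non-contact, or of missing day-29 status among discharged participants. A range of rates is used below.

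**Reproducing the plan.** The Whitehead formula is N = 12(z₀.₉₇₅ + z₀.₈₅)² / [(ln OR)² (1 − Σp̄ᵢ³)], where p̄ᵢ is the mean of the two arms' proportions in category i. At OR 1.75 the drug arm is 55.9, 31.6, 5.3, 4.3, 1.2, 0.6, 1.2% and 1 − Σp̄ᵢ³ = 0.840, so N = 12 × 8.978 / (0.3132 × 0.8401) = 409.5, against 412 in Table 5. At OR 2 it gives 269.7, against the plan's statement of "the odds ratio of 2 which required enrolment of 272 participants". Both agree closely.

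Power is Φ(√[N(1 − Σp̄ᵢ³)/12] × ln OR − 1.96). For N = 400 and OR 1.75 it is Φ(5.292 × 0.5596 − 1.96) = 84.2%, against about 85% stated. This match uses all 400 outcomes. With 9% lost (364 evaluable) power is 80.6%.

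**Effect of the fill.** A fraction m of discharged participants (categories 1 and 2) is taken as missing, unrelated to which of the two they are in, and is set to category 2. Category 1 then shrinks to (1 − m) of its size and categories 3 to 7 do not change. For 9% drug and 3% placebo:
- placebo category 1: 42 × 0.97 = 40.7%; category 2: 39.3%
- drug category 1: 55.9 × 0.91 = 50.9%; category 2: 36.6%

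A proportional-odds model fitted by maximum likelihood to these proportions gives OR 1.57. Here 1 − Σp̄ᵢ³ = 0.849, so power = Φ(5.319 × ln 1.566 − 1.96) = 66%. The same steps at other rates give:

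| Missing among discharged, drug/placebo | OR when truth is 1.75 | Power | OR when truth is 1 |
|---|---|---|---|
| none | 1.75 | 84% | 1.00 |
| 2%/1% | 1.71 | 81% | 0.99 |
| 5%/2% | 1.65 | 76% | 0.97 |
| 9%/3% | 1.57 | 66% | 0.93 |
| 9%/9% | 1.69 | 80% | 1.00 |
| 3%/9% | 1.87 | 91% | 1.07 |

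Under no effect, 9%/3% gives a two-sided type I error of 6.6%, of which about 5.6% is false harm and 1.0% false benefit (nominal 2.5% each). With 3%/9% these two swap. Balanced loss costs far less than unbalanced loss.

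**Direction.** If the participants filled in the drug arm are really in categories 3 to 7 (for example an undetected readmission), the fill favours drug. Under no effect, 2%, 5% or 9% of the drug arm filled this way gives OR 1.04, 1.11 or 1.20. This is an upper bound, because the rule applies only to participants taken to be discharged and alive.

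**The case against.** The strongest reply is that the exposed group is small. A participant must have stopped drug, been discharged alive, been judged not appropriate to ask, and not truly be in category 2. The default in Protocol 7.11 is that they will be asked, expressly to support intention to treat. Deaths and inpatient status come from records, and withdrawals are to be described by treatment and outcome. All of this stands, and it limits the size of the problem. It does not remove it: the description would show an imbalance but not correct the odds ratio, and the distinction between categories 1 and 2 still depends on the contact.

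Three stronger readings are tempting, and the documents do not support them.

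- A reader might infer that every missing outcome after stopping drug becomes category 2. SAP 7.4 fills only those discharged and alive. Other patterns have no SAP rule, which is a gap of a different kind.
- A reader might take OR 1.57 and 66% power as the expected damage. The 9% equals the allowance for all loss in the 300-participant design, here placed on one arm, and the 3% has no source in the documents. The rates also cover all missing day-29 status among discharged participants, of which investigator discretion is only one cause. If those who stop drug are more often truly in category 2, the fill is closer to correct and the bias shrinks.
- A reader might conclude that the one-dose condition should simply be struck out. Protocol 8.7 and Appendix 4 define day 1 as the day of first dose, so day 29 has no meaning for an undosed participant.

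**Conclusion.** The point holds as a design weakness that should be corrected. Protocol 7.11 makes post-discontinuation outcomes depend on an undefined judgement, which can create missing data related to tolerability or prognosis. SAP 7.4 then covers one missing pattern with a single value and has no analysis to test it, and the complete-case analysis and multiple-imputation option of Protocol 10.5 are not carried forward.

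The size is not known from the documents. Over the assumed rates, a true odds ratio of 1.75 is estimated at between 1.57 and 1.87. Mild imbalance (2%/1%) costs about 3 points of power, and marked imbalance (9%/3%) about 18. The bias can run for or against the drug. These figures rest on the Table 4 planning distribution, on missingness unrelated to category among discharged participants, and on rates that are assumptions. The blinded December 2020 distribution is not in the documents. It cannot be concluded that bias occurred, or that it would favour either arm.

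**What to change.** In Protocol 7.11, delete the clause that makes follow-up subject to the CI's or PI's opinion. State that every participant in the analysis population is followed to day 29 whether or not drug is continued, unless the participant declines, and that vital and hospital status are then taken from records where consent allows.

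In the SAP:
- include the complete-case analysis already promised in Protocol 10.5, and say whether multiple imputation will be used;
- give a rule for missing status in participants who are not known to be discharged and alive;
- add sensitivity analyses that replace the category 2 fill with category 1 and with worse categories;
- report missing day-29 status after drug discontinuation by arm.

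Separately, reconcile the one-dose condition with the population definitions in Protocol 10.2, Protocol 10.5 and SAP 7.2.1. If undosed participants are to be included, a time origin other than first dose is needed.

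The cost is a few extra day-29 calls and a little more analysis. Recruitment was expected to end in January 2021 and the SAP is dated 5 April 2021. If follow-up had already finished by then, the protocol wording could no longer help and the SAP changes are the part that remains workable.

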7.12. Storage and analysis of clinical samples

Storage and analysis of samples will only occur at the Tayside and Sheffield sites. The anonymisation, processing and storing of these specimens will be detailed in a local Laboratory Manual.

Sheffield:

- Will collect blood samples as per Schedule of Procedures, Appendix 4.
- Neutrophil function studies will be carried out at the Sheffield site.
- Blood will be processed and stored at Sheffield for later transfer to the Tayside laboratory for further analysis. Excess may be stored in the Tayside laboratory for future research use after trial results have been obtained.

Tayside:

- Will collect blood, sputum, endo-tracheal and nasal swab samples as per Schedule of Procedures, Appendix 4.
- Will carry out analysis as per exploratory end points.
- Preparations of blood, sputum and nasal swabs may be stored for future research use after trial results have been obtained.
- Excess biological samples that are being taken for clinical reasons may be stored for future use if no longer required for clinical purposes

7.13. End of trial

The end of trial is defined as completion of day 29 assessments for last participant at all sites. The Sponsor and/or CI have the right at any time to terminate the trial for clinical or administrative reasons.

The end of the trial will be reported to the Sponsor, REC, MHRA and NHS R&D Office(s) within 90 days, or 15 days if the trial is terminated prematurely. The CI will ensure that any appropriate follow-up is arranged for all participants.

A final clinical trial report will be submitted to the MHRA via EudraCT within 1 year of the end of the trial and will also be provided to the Sponsor and REC.

